7.6 Variables to be Measured to Demonstrate Achievement of Endpoints

The endpoints and measures will be assessed as described in Table 7.6-1.

Table 7.6-1. Assessment of Endpoints and Measures

Endpoint / Measure	Assessment ¹
Hernia recurrence	Clinical examination
Rate of adverse events	Evaluation based upon reports of events submitted by the study sites
Rate of Surgical Site Occurrences (SSO)	Evaluation based upon reports of occurrences submitted by the study sites
Rate of Surgical Site Occurrences needing Intervention (SSOPI)	Evaluation based upon reports of occurrences submitted by the study sites

Patient quality of life	Postoperative assessment (patient questionnaire)
-------------------------	--

¹For the 1 and 2-year follow-up visits: Every attempt should be made to have the patient return for a physical exam at the 1-year and 2-year timepoints in order to determine hernia recurrence. Results from a physical exam made by a non-study physician (e.g. primary care physician) can be included if assessment at the clinical site is not possible.

If the patient refuses or is unable to return in person for the 1-year or 2-year physical exam, patient self-assessment of the presence of recurrence symptoms, patient responses regarding adverse events, and patient questionnaires may be obtained via telephone or email. If the patient self-assessment of the presence of recurrence symptoms suggests that a hernia is present, the patient should be contacted and requested to return for a physical exam for confirmation.

Patient reported outcomes will be tabulated and reported. The primary endpoint will be analysed as noted in Section 11.0.

Patient data will be documented by trained personnel at the clinical site and recorded onto eCRFs through an electronic data capturing (EDC) system. The assessment schedule is summarized in Table 7.6-2 and in Appendix B:

Table 7.6-2. Assessment schedule

	Pre-Procedure	Procedure	Follow-up			
			30 days (± 15 days)	6 month (± 30 days)	1 year (± 90 days)	2 years (± 90 days)
Consent	X					
Medical history	X					
Procedure Information		X				
Physical exam	X	X	X	X	X	X
Patient Reported Outcomes measures			X	X	X ^a	X ^a
Adverse events		X	X	X	X ^a	X ^a

^a Every attempt should be made to have the patient return for a physical exam at the 1-year and 2-year timepoints in order to determine hernia recurrence. Results from a physical exam made by a non-study physician (e.g. primary care physician) can be included if assessment at the clinical site is not possible. If the patient refuses or is unable to return in person for the 1-year or 2-year physical exam, patient

self-assessment of the presence of recurrence symptoms, patient responses regarding adverse events, and patient questionnaires may be obtained via telephone or email.

8.0 Eligibility Criteria

Patients will be selected in accordance with the device's labeled indication and according to the Manufacturer's Instructions for Use.

Inclusion Criteria

Patients who meet the following criterion are suitable for receiving a Biodesign Hernia Graft, and are therefore suitable for inclusion in this study:

1. Primary or recurrent ventral hernia in need of surgical repair

Exclusion Criteria

According to the IFU, the Biodesign Hernia Graft should not be used in patients with known sensitivity to porcine material. Therefore, the following patients will be excluded from the study:

1. Known sensitivity to porcine material

For the purpose of the study, the following patients will also be excluded:

2. Age < 18 years
3. Unable or unwilling to provide informed consent
4. Life expectancy of less than one year from the date of the index procedure

Patients will be excluded from the study if they never receive a Biodesign Hernia Graft during their index procedure.

8.1 Patient Consent

Patients who meet all of the inclusion criteria and none of the exclusion criteria will be invited to participate in this study. Patients eligible for enrollment will have the clinical study explained to them, as well as the potential risks and benefits of their participation in the study, at a time point sufficiently prior to study participation to allow the patient adequate time to fully consider their participation in the study. All information pertinent to the study will be provided in writing in a language understandable to the patient. Each patient who decides to participate will sign and date an informed consent document prior to the procedure or any study-specific assessments. If new information is obtained, patients who have not exited the study will be informed about the new information, and will be re-consented if required by the clinical site's IRB.

9.0 Methods

9.1 Pre-procedure Evaluation

Prior to patient enrollment, patients will undergo a baseline evaluation. Assessments will be completed as described in Table 9.1-1. All pre-procedure assessments are considered standard of care.

Table 9.1-1. Pre-procedure requirements

Pre-procedure	
Timing	Prior to the study procedure
Type	In-person
Assessment	Review study with patient and obtain written informed consent
	Clinical assessment including hernia assessment and symptomology
	Record patient demographics and pre-op evaluation

9.2 Point of Enrollment

Patients are considered enrolled in the study when the device implant procedure is completed.

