5.0 Background Information

The Biodesign Hernia Graft is comprised of 8 layers of decellularized porcine small intestinal submucosa (SIS) that has been pressed-lyophilized (i.e., freeze-dried under vacuum pressure) to laminate the component sheets (i.e., layers) together. In addition, it is perforated and sewn with 4-0 Trisorb suture (polyglycolic acid (PGA); Samyang Corporation, Seoul, South Korea). The suture is distributed in a diamond pattern across the graft and along the periphery and is intended to mitigate delamination of the layers upon rehydration and/or manipulation during implantation. Being a completely biologic device, the Biodesign Hernia Graft is considered MR safe.

The Biodesign Hernia Graft is available in eight (8) sizes: 8 cm x 10 cm, 8 cm x 20 cm, 8 cm x 30 cm, 10 cm x 10 cm, 13 cm x 15 cm, 13 cm x 22 cm, 20 cm x 20 cm, and 20 cm x 30 cm. The graft is terminally sterilized using an established ethylene oxide (EtO) sterilization cycle that has been validated to a sterility assurance level of 10^{-6} . Sterilization is routinely monitored, calibrated, and operated in adherence with standardized procedures. The Biodesign Hernia Graft may be stored at room temperature

in a clean, dry location for up to 18 months.

The Biodesign Hernia Graft is a technology that has been used in the treatment of hernias and abdominal wall defects for nearly 10 years. This post-market clinical follow-up study is being performed to confirm the continued safety and performance of the Biodesign Hernia Graft when used in accordance with its approved labeling.

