7.5.2 Additional Measures

Additional measures will include the following:

- Device-, procedure-, and hernia-related adverse event rates through the 2-year follow-up period
- Hernia recurrence rate through 2-year follow-up
- Operative times
- Duration of hospital stay
- Hospitalization times for related SAEs
- Patient-reported quality of life

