11.4 Planned Subgroups and Covariates

All patients enrolled in the study, except patients whose device is damaged in a subsequent procedure prior to reaching the primary efficacy endpoint, will be included for the primary analyses. If warranted, baseline characteristics (including but not limited to: patient demographics and hernia type) and procedural details (including but not limited to: procedure type (laparoscopic or open), surgical repair technique, fascial closure, and location of device placement) will be analyzed to determine their impact on the hernia recurrence rate.

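### Enrolment waits for a completed implant and no safety population is defined, so attempted but abandoned implants have no stated place in the adverse event rates

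*Combined protocol and SAP*

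**What the plan says.** Consent comes before surgery: each participant "will sign and date an informed consent document prior to the procedure or any study-specific assessments" (Section 8.1). Enrolment comes later. Section 9.2 states: "Patients are considered enrolled in the study when the device implant procedure is completed". Section 8.0 adds: "Patients will be excluded from the study if they never receive a Biodesign Hernia Graft during their index procedure".

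The primary analysis set in Section 11.4 is "All patients enrolled in the study, except patients whose device is damaged in a subsequent procedure prior to reaching the primary efficacy endpoint". Section 11 names no population for adverse events, and it plans no count of consented patients in whom implantation was attempted but not completed.

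The safety summary is described in Section 7.5.2 as "Device-, procedure-, and hernia-related adverse event rates through the 2-year follow-up period". Section 5.0 gives the purpose of the study as being to "confirm the continued safety and performance of the Biodesign Hernia Graft when used in accordance with its approved labeling". Section 3.0 asks for adverse event rates under ordinary commercial use.

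**The concern.** Handling and placing the graft is part of using it. Section 5.0 recognises a possible problem at that stage: the suture pattern "is intended to mitigate delamination of the layers upon rehydration and/or manipulation during implantation". If a graft is abandoned for that or any other reason, or the operation stops early, the patient has consented and been exposed to the procedure but does not meet the enrolment definition.

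With no safety population to bring such a patient back in, implant-stage device and procedural events could drop out of the rates the study exists to report. The reader of the final report would also have no count showing how many such cases there were.

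**Working it through.** **Where an attempted but uncompleted implant falls.**

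1. Consent signed: yes, before surgery (8.1).
2. Enrolled: no, because the implant procedure was not completed (9.2).
3. Excluded: yes under 8.0 if no graft was received. Neither 8.0 nor 9.2 says how to treat a graft placed and then removed in the same operation.
4. In the primary analysis: no, because 11.4 starts from enrolled patients.
5. In the adverse event rates: not stated. Table 7.6-2 and Appendix B schedule adverse events from the procedure onward, and Section 9.3 records peri-operative details on the eCRFs, but nothing places a non-enrolled patient in a numerator or denominator.

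**The plan's own figures.** The plan gives no abandonment rate and no expected adverse event rate for this study, so there is no stated figure to reproduce on this point. The sample size matters only for the fix. Section 11.1 gives 86 evaluable patients. That is the smallest n at which a two-sided 95% Wilson interval has both limits within 10 points of the estimate with probability at least 0.8, when the true proportion is 0.801 (probability 0.82 at 86, 0.76 at 85). The target of 95 matches 86 × 1.10 = 94.6. The margin for loss to follow-up is 95 − 86 = 9.

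**Effect on an adverse event rate.** Let x of n completed implants have a related event, and let k attempts be omitted, of which e had a related event. The reported rate is x/n; the rate over all attempts is (x + e)/(n + k). Take n = 95 and, purely for illustration, x = 5.

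| Omitted k | With event e | Rate over all attempts |
|---|---|---|
| 0 | 0 | 5/95 = 5.3% |
| 1 | 1 | 6/96 = 6.25% |
| 3 | 3 | 8/98 = 8.2% |
| 5 | 5 | 10/100 = 10.0% |
| 3 | 1 | 6/98 = 6.1% |
| 3 | 0 | 5/98 = 5.1% |

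- One omitted patient with an event moves the rate by (n − x)/[n(n + 1)] = 90/(95 × 96) = 0.99 points upward.
- One omitted patient without an event moves it by x/[n(n + 1)] = 5/(95 × 96) = 0.05 points downward.
- The rate rises only if e/k exceeds x/n.

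**Size of the unreported group.** With 95 completed implants and 1, 2, 5 or 10 abandoned attempts (assumed), the proportion not implanted, k/(95 + k), is 1.0%, 2.1%, 5.0% or 9.5%. The exact 95% intervals are 0.0–5.7%, 0.2–7.3%, 1.6–11.3% and 4.7–16.8%.

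**The case against.** The strongest reply is that the documents never restrict adverse event rates to enrolled patients. Section 11.4 governs the primary analyses, which concern recurrence. Event collection begins at the procedure, and Section 10.1 lets a patient withdraw before or after the procedure and asks for the data up to that point. So some consented patients are treated as participants before the enrolment point in 9.2. This stands: exclusion from the safety rates is an inference, and the exact statement is that the safety denominator is undefined.

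A reader might infer four stronger things that the documents do not support.

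- **That the rates cover only successful implants.** The criterion in 9.2 is completion. Complications during or after a completed implant are counted, and a patient whose first graft fails but who then receives a second study graft has received a graft and would enter.
- **That any bias must favour the device.** An omitted attempt with no related event slightly lowers the rate, as 5/98 shows. Under the definition in Section 9.5, a torn or ill-fitting graft discarded without harm need not be an adverse event. The 8.2% and 10.0% rows therefore hold only if every omitted patient had a related event.
- **That the recurrence conclusion is at risk.** If abandoned attempts were scored as failures on top of the assumed 19.9% recurrence, the combined rate would reach the 22% threshold of Section 11.3 at (0.22 − 0.199)/(1 − 0.199) = 2.6% abandonment. Appendix C defines recurrence as a hernia finding at the repaired site, so that composite is not the protocol's endpoint.
- **That such cases are known to occur.** Section 5.0 describes a design feature and gives no frequency. The omitted group could be empty.

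**Conclusion.** The point holds in a limited form. Entry conditional on a completed implant, together with the absence of a safety population, leaves attempted but abandoned or uncompleted implants without a stated place in the device- and procedure-related event rates. This sits badly with a study meant to confirm continued safety in ordinary use.

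Size and direction are unknown because no abandonment rate is given. The effect is nil with no such cases. The per-patient shifts of about 1 point up and 0.05 points down assume 95 completed implants and 5 events, a count chosen only for illustration. One-year recurrence is essentially untouched, since a patient without the graft has no graft-reinforced repair to assess. The sample size of 86 evaluable and 95 enrolled does not depend on this point.

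**What to change.** - Keep the target of 95 and the recurrence analysis for patients who leave the operating room with a graft.
- Add to Section 11 a safety population: all consented patients in whom the study graft was opened for use or implantation was attempted.
- Amend 9.2 and 8.0 so that these patients' procedural data and adverse events are recorded and enter the device- and procedure-related rates, without counting toward the 95.
- Report the number attempted but not implanted, with reasons.
- State how a graft placed and removed in the same operation is classified.

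Keeping these patients outside the 95 matters. If 5 attempts used places under the cap, 95 − 5 = 90 implants would remain, and losing the allowed 9 would leave 81 evaluable, below 86.

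The cost is wording in Sections 8.0, 9.2 and 11, one eCRF field, a few extra records, and a statement of how long non-implanted patients are followed for events. The reported event rates may come out slightly less favourable. Consent already precedes surgery, so its timing need not change.

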9.3 Study Procedure

The patient will undergo repair of a ventral hernia with the implantation of the Biodesign Hernia Graft, and any other concomitant procedures that are clinically indicated. Presence of hernia will be confirmed intra-operatively and classified using the European Hernia Classification System.

The device will be implanted according to the IFU.

Peri- and post-operative patient treatment will be conducted in accordance with surgeon discretion and institutional standard of care. All peri- and post-operative details will be documented and recorded on the eCRFs within the EDC system.

Discharge following the procedure will be in accordance with surgeon discretion and institutional standard of care. Patients should be given instructions to refrain from activity that may complicate recovery.

9.4 Follow-up

Patients are expected to participate in this study for 2 years after the procedure. The follow-up visits will occur within the time frames listed below. Following the study procedure, assessments will be completed as described in Table 9.4-1.

Table 9.4-1. Follow-up requirements

30-day Follow-up (± 15 days)	
Timing	15-45 days following the study procedure
Type	In person
Assessments	Physical exam of the incision and abdominal wall
	Record specific data points within the EDC system
	Administer a postoperative assessment (patient questionnaire)
6- month Follow-up (± 30 days)	
Timing	153-213 days following the study procedure
Type	In person
Assessments	Physical exam of the incision and abdominal wall
	Record specific data points within the EDC system
	Administer postoperative assessment (patient questionnaire)
1-Year Follow-up (± 90 days)	
Timing	275 – 455 days following the study procedure
Type	In person ¹
Assessments	Physical exam of the incision and abdominal wall
	Record specific data points within the EDC system
	Administer postoperative assessment (patient questionnaire)
2-Year Follow-up (± 90 days)	
Timing	640 – 820 days following the study procedure
Type	In person ¹
Assessments	Physical exam of the incision and abdominal wall
	Record specific data points within the EDC system
	Administer postoperative assessment (patient questionnaire)

¹For the 1 and 2-year follow-up visits: Every attempt should be made to have the patient return for a physical exam at the 1-year and 2-year timepoints in order to determine hernia recurrence. Results from a physical exam made by a non-study physician (e.g. primary care physician) can be included if assessment at the clinical site is not possible.

If the patient refuses or is unable to return in person for the 1-year or 2-year physical exam, patient self-assessment of the presence of recurrence symptoms, patient responses regarding adverse events,

and patient questionnaires may be obtained from the patient via telephone or email. If the patient self-assessment of the presence of recurrence symptoms suggests that a hernia is present, the patient should be contacted and requested to return for a physical exam for confirmation.

Patient reported outcomes will be tabulated and reported. The primary endpoint will be analysed as noted in Section 11.0.

9.5 Adverse Events

An adverse event is any untoward medical occurrence, unintended disease or injury, or untoward clinical signs (including abnormal laboratory findings) in subjects (patients), users, or other persons, whether or not related to the medical device.

A Serious Adverse Event is an adverse event that:

- Led to death,
- Led to serious deterioration in the health of the subject (patient), that either resulted in:
 - A life-threatening illness or injury, or
 - A permanent impairment of a body structure or a body function, or
 - In-patient or prolonged hospitalization, or
 - Medical or surgical intervention to prevent life-threatening illness or injury or permanent impairment to a body structure or a body function,
- Led to fetal distress, fetal death, or a congenital abnormality or birth defect.

NOTE: Planned hospitalization for a pre-existing condition, or a procedure required by the study plan, without serious deterioration in health, is not considered a serious adverse event.

The EDC system allows for recording of adverse events and should therefore be used as the typical method of adverse event reporting. The study sponsor will periodically review adverse events that have been added to the EDC system and will process these events according to standard operating procedures. If an adverse event meets the criteria for reporting to a regulatory agency, the sponsor will contact the principal investigator and will perform a thorough investigation of the adverse event as required under applicable regulations. The sponsor is responsible for reporting events to the regulatory authorities, the reviewing IRB(s), and the principal investigator(s), as required according to applicable regulations/standards/policies.

Serious Adverse Events should be added to the EDC system and reported to the study sponsor within 3 calendar days of the study site becoming aware of the event.

The principal investigator will notify their IRB of applicable adverse events occurring for the duration of the study according to institutional guidelines.

10.0 Participation Endpoints of the Study

A patient's participation in the study will end after any of the following:

- Completion of all scheduled clinical evaluations through 2 years
- Subsequent procedure due to recurrence of the original hernia defect
- Any subsequent surgical procedure resulting in removal of the study device
- Patient withdrawal
- Principal investigator withdrawal of patient
- Patient loss to follow-up
- Patient death

After a patient exits the study for any reason, there are no study-specific requirements for follow-up and no additional data will be collected. Any data collected up to the point of patient exit may be used in the study.

10.1 Patient Withdrawal

A patient may decide to withdraw from the study at any time either before or after undergoing the study procedure without prejudice or loss of care. The principal investigator may also decide to withdraw the patient from the study at any time based on medical judgment. The principal investigator will ensure that the sponsor is notified of any patient withdrawal. In all instances of withdrawal, data collected up to the time of patient withdrawal, will be submitted and will include the reason why the patient has been withdrawn from the study (e.g. patient request).

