6.0 Risk Analysis and Risk Assessment

6.1 Risks and Possible Adverse Reactions

Foreseeable adverse events associated with the use of the Biodesign Hernia Graft and other biologic graft prostheses are described in the IFU and will be collected in this study and reported as an additional measure.

Please reference the IFU for the following:

- Contraindications
- Warnings
- Precautions

The use of this FDA cleared device does not introduce any new or additional risk to standard ventral hernia procedures using biologic mesh materials.

Because the Biodesign Hernia Graft is cleared for general use in this patient population, the only additional patient risk associated with participation in this study is accidental release of protected health information.

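### Investigator withdrawal on medical grounds ends all data collection in implanted patients, so 1-year recurrence status can go unobserved for reasons related to outcome

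*Combined protocol and SAP*

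**What the plan says.** Section 10.1 gives the investigator an open discretion, without criteria: "The principal investigator may also decide to withdraw the patient from the study at any time based on medical judgment". The sponsor must be told of every withdrawal, and the reason and the data to that date must be submitted.

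Section 10.0 lists "Principal investigator withdrawal of patient" among the events that end participation, and continues: "After a patient exits the study for any reason, there are no study-specific requirements for follow-up and no additional data will be collected". Earlier data are kept: "Any data collected up to the point of patient exit may be used in the study".

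Four other sections bear on this:

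- Section 9.2 places enrolment at completion of the implant procedure, so every enrolled patient has the graft.
- Section 6.1 says that "the only additional patient risk associated with participation in this study is accidental release of protected health information".
- Section 10.3 provides that, when a site or the study closes, treated patients are still followed to the primary endpoint.
- Sections 7.6 and 9.4 accept an outside physician's examination at 1 and 2 years or, failing that, self-assessment by telephone or email.

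On analysis, section 11.4 provides that all enrolled patients, other than those whose graft is damaged in a later operation "prior to reaching the primary efficacy endpoint, will be included for the primary analyses". Section 11.5 treats withdrawn patients as a source of missing data, covered by extra enrolment. It plans complete case, best-available-data and multiple-imputation analyses and names none of them as primary.

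**The concern.** The graft is implanted once, and later care follows the surgeon's judgment and local practice (9.3). Once a patient is enrolled there is no continuing study treatment to stop, and the documents give no participation-risk reason for ending follow-up. Even so, a medical event can lead an unblinded investigator to withdraw the patient, and the outcome is then no longer sought. Closure of a site, which has nothing to do with the individual patient's outcome, brings a stricter duty to follow up than a medically prompted exit does.

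The study has one arm and a fixed threshold: the null hypothesis in section 11.3 is a recurrence rate of 22% or more. No control group shares the bias. If patients with a complicated course are withdrawn more often and also recur more often, the observed rate is too low. Adverse event reporting through 2 years is shortened in the same patients.

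**Working it through.** **Inputs.** 95 enrolled, 86 from the sample size calculation, planning recurrence 19.9% (100 − 80.1), all from section 11.1; threshold 22% (11.3); 95% confidence interval (11.2). The allowance for loss is 95 − 86 = 9 patients, or 9/95 = 9.5%; no loss rate is stated.

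**The plan's own figure.** With success 0.801 against 0.901, two-sided alpha 0.05 and power 0.80:

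n = [(1.960 × √(0.901 × 0.099) + 0.842 × √(0.801 × 0.199)) / 0.10]² = 84.9, or 85, close to the stated 86.

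This point does not rest on 86 or 95. They only set the scale.

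**Assumptions.** The goal is met if the upper limit of the two-sided 95% interval is below 22%. The interval is exact (Clopper-Pearson); the plan names no method. The number withdrawn (w) and their recurrence risk (r) are not in the documents, so a range is shown.

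**Step 1: does a planned analysis recover the outcome?** The self-report rules in section 11.5 need a self-assessment of recurrence symptoms, and none is collected after exit. Complete case analysis omits the patient. Multiple imputation keeps the patient, but corrects only as far as recorded data explain the withdrawal. Section 11.5 first commits to it and later says only that it will be considered. No worst-case or tipping-point analysis is planned.

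**Step 2: bias at the null boundary.** With a true rate of 22%, expected recurrences are 95 × 0.22 = 20.9. The expected complete case rate is (20.9 − w × r) / (95 − w). For w = 3, r = 0.60: (20.9 − 1.8) / 92 = 20.8%. For w = 9, r = 0.60: (20.9 − 5.4) / 86 = 18.0%. The type I error is the binomial probability, at that rate, of a count that meets the goal: at most 12 of 95, 12 of 92, 11 of 90 or 11 of 86. With no withdrawals it is 1.5%.

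| Withdrawn | Their recurrence risk | Observed rate | Type I error |
|---|---|---|---|
| 3 | 19.9% | 22.1% | 2.0% |
| 3 | 40% | 21.4% | 2.9% |
| 3 | 60% | 20.8% | 4.0% |
| 3 | 100% | 19.5% | 7.3% |
| 5 | 19.9% | 22.1% | 1.2% |
| 5 | 40% | 21.0% | 2.3% |
| 5 | 60% | 19.9% | 4.0% |
| 5 | 100% | 17.7% | 10.9% |
| 9 | 19.9% | 22.2% | 2.0% |
| 9 | 40% | 20.1% | 5.4% |
| 9 | 60% | 18.0% | 12.9% |
| 9 | 100% | 13.8% | 46.5% |

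The 19.9% rows show that small shifts come from the discrete counts alone; there the bias is at most +0.2 points.

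**Step 3: near the boundary.** 13/95 = 13.7%, exact upper limit 22.3%, goal missed. If one of the 13 is withdrawn before the recurrence is recorded, 12/94 = 12.8%, upper limit 21.2%, goal met.

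**Step 4: away from the boundary.** 19/95 = 20.0% is close to the planning rate, with exact upper limit 29.5%. Three such withdrawals give 16/92 = 17.4%, upper limit 26.7%. The goal is missed both times. Eight would be needed to cross the threshold (11/87, upper limit 21.5%).

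**Step 5: interval method.** The Wald upper limit is p + 1.96 × √(p(1 − p)/n). For 13/95 it is 0.1368 + 1.96 × √(0.1368 × 0.8632 / 95) = 20.6%, already met. The Wald boundary lies between 14/95 (21.9%) and 15/95 (23.1%), and removing one recurrence from the latter (14/94, 22.1%) does not cross it. The boundary count therefore depends on a choice that the plan leaves open.

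**The case against.** The strongest reply is that the plan already limits the damage. Withdrawal is not an exclusion under section 11.4. A recurrence recorded before exit still counts. The sponsor is notified and receives the reason for each withdrawal, and serious adverse events are reported within 3 calendar days of the site becoming aware (9.5), so misuse would be visible. Nothing suggests that investigator withdrawals will be frequent. Scheduled visits can also become unreasonable for a very ill patient: section 6.1 speaks of risk, not burden.

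Most of this stands, and it rules out several stronger readings:

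- A reader might infer that withdrawn patients leave the primary analysis. Section 11.4 keeps them. They are lost only from the complete case analysis and perhaps from the per-protocol and analyzable sets, which section 11.5 does not define.
- A reader might infer that multiple imputation gives them average risk. The imputation model is left open, and one that uses recorded complications need not do so.
- A reader might infer that one withdrawal can generally decide the study. That holds only near the boundary.
- A reader might infer that withdrawal on medical grounds should be banned. Burden is a legitimate reason to stop visits.

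The safeguards still do not supply the missing outcome. They document the loss, while section 10.0 prevents its recovery even when the patient would agree to a telephone call.

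**Conclusion.** The point holds in limited form. The rules in sections 10.0 and 10.1 allow outcome-related loss of 1-year status in implanted patients, without a participation-risk reason and against the standard that section 10.3 sets for closure. No planned analysis is sure to correct it.

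The direction is downward for recurrence only if withdrawn patients recur more often than those who stay. The size cannot be fixed from the documents. With complete cases, the exact interval and a true rate of 22%, three withdrawals at 60% recurrence lower the observed rate by 1.2 points (22.0 − 20.8) and raise the type I error from 1.5% to 4.0%. Nine, the whole allowance, lower it by 4.0 points and raise the error to 12.9%. At about the planning rate the bias is negligible. This is a cheap improvement to make, not a flaw that invalidates the study.

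**What to change.** **Sections 10.0 and 10.1.** Separate stopping study visits from ending data collection. For implanted patients whom the investigator withdraws and who have not withdrawn consent, continue to seek recurrence status and adverse events at 1 and 2 years by telephone, email or an outside physician's examination, as sections 7.6 and 9.4 already allow. Offer the same option to patients who withdraw themselves. Their right to refuse is unchanged.

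**Section 11.5.** Add a sensitivity analysis that counts investigator-withdrawn patients with unknown 1-year status as recurrences, or a tipping-point analysis. In the step 3 example, the first would turn 12/94 back into 13/95 and show that the conclusion depends on one patient.

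**Cost.** A few more follow-up contacts, one consent option and one extra analysis. The worst-case count will overstate recurrence when some withdrawn patients have not recurred, so it belongs among the sensitivity analyses.
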